7.8 Handling of Data

7.8.1 Data Management

The data management for this study will be provided by Synteract. All data reported on case report forms will be double-entered into a clinical database system. A series of computerized edit checks will be run to identify missing data, inconsistent data, and errors in the clinical database. A description of these procedures is provided in the Data Management and Data Quality Plan (document on file).

7.8.2 Incomplete Adverse Event Start Dates

Missing and incomplete AE start dates will be imputed based on the algorithm described below. The algorithm will be used only if the end date of the AE (if reported) indicates the event was not resolved before the first administration of study drug. The purpose of the imputation is to determine for purposes of analysis if an AE with missing or incomplete start date is treatment emergent (as defined in Section 9.6.1). Imputed AE dates will not be used to calculate the duration of AE episodes.

A list of incomplete and imputed dates will be prepared by the statistical programmer and will be submitted to the statistician for review. Missing and incomplete AE end dates will not be imputed.

Algorithm for Imputation of Incomplete/Missing Adverse Event Start Dates

Case 1:

IF YEAR PORTION OF AE START DATE = MISSING THEN MISSING AE
START DATE = FIRST DOSE DATE;

Case 2:

```
IF YEAR PORTION OF AE START DATE = YEAR PORTION OF FIRST  
DOSE DATE THEN DO;  
  
IF MONTH PORTION OF AE START DATE = MISSING THEN MISSING AE  
START DATE = FIRST DOSE DATE;  
ELSE  
  
IF MONTH PORTION OF AE START DATE = MONTH PORTION OF FIRST  
DOSE DATE THEN MISSING AE START DATE = FIRST DOSE DATE;  
  
ELSE  
IF MONTH PORTION OF AE START DATE ≠ MONTH PORTION OF FIRST  
DOSE DATE THEN MISSING AE START DATE = MDY(AE START  
MONTH, 1, AE START YEAR);  
END;
```

Case 3:

```
IF YEAR PORTION OF AE START DATE > YEAR PORTION OF FIRST  
DOSE DATE THEN DO;  
  
IF MONTH PORTION OF AE START DATE = MISSING THEN MISSING AE  
START DATE = MDY(1, 1, AE START YEAR);  
  
ELSE  
IF MONTH PORTION OF AE START DATE ^= MISSING THEN MISSING  
AE START DATE = MDY(AE START MONTH, 1, AE START YEAR);  
END;
```

7.8.3 Prior and Concomitant Medication Start Dates

Incomplete start dates for concomitant medications will be imputed in the same manner as AEs.

In determining if a medication is prior or concomitant, the following code will be used:

```
*IF STARTED BEFORE TRTSTDT;  
  IF STRDT_S < TXST_S THEN PRIOR = 'Y';  
  
*IF STOPPED BEFORE TRTSTDT OR NO DATE REPORTED AND  
  CONTINUED.;  
  IF STPDT_S < TXST_S AND CONT = '' THEN PRIOR = 'Y';  
  
* IF STARTED ON/AFTER TRTSTDT;  
  IF STRDT_S >= TXST_S THEN PRINT= 'N';  
  
* IF STOPPED ON/AFTER TRTSTDT OR CONTINUED.;  
  IF STPDT_S >= TXST_S OR CONT = 'Y' THEN PRIOR= 'N';
```

NOTE: STRDT__S=START DATE FOR MEDICATION

TXST__S = treatment start date

CONT='Y' = medication is continuing

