7.6.2 Concomitant Medications

Concomitant chemotherapies will be collected and coded using WHODDE version March 1, 2010. All chemotherapy agents will be listed individually and summarized by anatomical therapeutic class and generic name.

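### SAP 7.8.3 assigns PRINT instead of PRIOR in its prior/concomitant code, so an on-study agent with a missing stop date and blank CONT is labelled prior

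*SAP*

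**What the plan says.** SAP 7.8.3 states that its code will be used to decide whether a medication is prior or concomitant. In order, the four statements are:

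1. "IF STRDT_S < TXST_S THEN PRIOR = 'Y"
2. "IF STPDT_S < TXST_S AND CONT = '' THEN PRIOR = 'Y"
3. "IF STRDT_S >= TXST_S THEN PRINT= 'N"
4. "IF STPDT_S >= TXST_S OR CONT = 'Y' THEN PRIOR= 'N"

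The note below the code explains the continuation flag: "CONT='Y' = medication is continuing". On incomplete dates the section says only this: "Incomplete start dates for concomitant medications will be imputed in the same manner as AEs". It gives no rule for medication stop dates. The adverse event rule that it borrows, in SAP 7.8.2, says "Missing and incomplete AE end dates will not be imputed".

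The medications concerned are chemotherapies. SAP 7.6.2 plans this for them: "All chemotherapy agents will be listed individually and summarized by anatomical therapeutic class and generic name". SAP 7.1 names SAS version 9 or later as the software.

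**The concern.** Three of the four statements write to PRIOR. The third writes to PRINT, a name that appears nowhere else in the SAP, although the comment above it describes drugs started on or after treatment start. The statement that should declare an on-study start not prior therefore has no effect on the flag.

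That would be harmless if the other statements always reached the right answer, but they do not when the stop date is missing. The second statement can then label a drug prior even though its own start date shows that it began on study.

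What is at stake is the accuracy of that label. Protocol 6.4.2 allows approved antitumour agents to be added when progression is a concern. A reader of the chemotherapy output would want to know which agents were given alongside carfilzomib in this study and which came before it.

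**Working it through.** The plan states no figure here, so the check is to run the rule on each kind of record.

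**Inputs**
- The four statements in their written order, and the meaning of CONT (SAP 7.8.3).
- Start-date imputation only (SAP 7.8.3, with the algorithm in 7.8.2). A start date with no year becomes the first dose date. So does one in the year of first dose with the month missing, or one in the month of first dose with the day missing.
- SAS (SAP 7.1), where a missing numeric value compares as lower than any date.
- Assumptions: PRIOR is blank before the code runs, and a partial stop date, having no imputation rule, reaches the code as missing.

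**Trace of the failing record.** Set first dose at day 0. Take a start on day 30, stop missing, CONT blank.
- Statement 1: 30 < 0 is false, so PRIOR stays blank.
- Statement 2: missing < 0 is true and CONT is blank, so `PRIOR='Y'`.
- Statement 3: 30 >= 0 is true, so `PRINT='N'` and PRIOR stays `'Y'`.
- Statement 4: missing >= 0 is false and CONT is not `'Y'`, so there is no change.
- Result: `PRIOR='Y'` for a drug that started on study.

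**All feasible patterns.** Stops before starts are excluded, as are records with both a stop date and `CONT='Y'`.

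| Start day | Stop day | CONT | PRIOR as written | PRIOR with PRINT changed to PRIOR |
|---|---|---|---|---|
| -10 | missing | blank | Y | Y |
| -10 | missing | Y | N | N |
| -10 | -5 | blank | Y | Y |
| -10 | 60 | blank | N | N |
| 0 | missing | blank | **Y** | **N** |
| 0 | missing | Y | N | N |
| 0 | 60 | blank | N | N |
| 30 | missing | blank | **Y** | **N** |
| 30 | missing | Y | N | N |
| 30 | 60 | blank | N | N |

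Two of the ten rows change, and both are on-study starts with stop missing and CONT blank. The day 0 row also covers a drug whose missing start date has been imputed to first dose.

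**Sensitivity to the SAS ordering.** If a missing stop date did not satisfy the less-than test, statement 2 would not fire and the record would end with PRIOR blank. That is still not `'N'`, so the third statement is needed either way.

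**Is a non-missing check in statement 2 also needed?** With statement 3 corrected, a start before first dose (or a start still missing) is already set to `'Y'` by statement 1. A start on or after first dose is set to `'N'` by statement 3. The check then changes no result. Used alone, without the correction to statement 3, it would leave the two failing rows blank.

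**The case against.** The strongest reply is that this is a one-word slip beneath a comment that makes the intent plain, in a descriptive single-arm study that tests no hypothesis (Protocol 10.1), and that little depends on it. Much of that stands.

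- A reader might infer that misflagged agents drop out of the chemotherapy summary. The documents do not say so. SAP 7.6.2 lists and summarises all chemotherapy agents and does not make either output conditional on PRIOR. The supported consequence is a wrong label.
- A reader might infer that the error obscures how far safety and efficacy reflect carfilzomib alone. The SAP does not link the flag to those analyses. Regimen changes come from their own case report form (SAP 7.4). The baseline reset (5.5), PFS (7.7.2), TTP (7.7.3) and the adverse event tables (7.6.1) do not use PRIOR. One limit is that 7.4 describes added drugs as anti-myeloma agents, so it is less explicit for the solid tumour cohort.
- A reader might infer that such records are common. No count is given. SAP 7.8.1 plans computerised checks for missing and inconsistent data, and a drug recorded as neither stopped nor continuing is a natural query.

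None of this removes the error. The SAP says that this code will be used, and on one definite pattern it returns an answer that contradicts the record's own start date.

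**Conclusion.** The rule is wrong as written, with a narrow effect. Every medication that starts on or after first dose (including by imputation) and has a missing stop date and blank CONT is labelled prior. On-study agents with a complete stop date, or with `CONT='Y'`, are labelled correctly.

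The consequence is limited to the prior/concomitant label of on-study chemotherapy agents. No primary or secondary endpoint is affected by anything the SAP states. The number of affected records cannot be determined from the documents and could be zero.

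The `'Y'` result rests on SAS ordering of missing values. Its extension to partial stop dates rests on their reaching the code as missing, since the SAP is silent on that.

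**What to change.** In the third statement of SAP 7.8.3, change PRINT to PRIOR. This is sufficient on its own: it corrects both failing patterns and leaves the other eight unchanged. An explicit non-missing check on STPDT_S in the second statement is optional. It makes the intent clearer but changes no further result.

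Add one sentence saying how missing or partial medication stop dates are handled. At the same time, reconcile the comment above the second statement, which speaks of a medication with no date that is continued, with the code, which requires CONT to be blank.

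The cost is one word of code and a sentence or two of text. No data collection or other analysis changes.
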